9.1. Extent of Exposure

Duration of exposure will be summarized using descriptive statistics. The duration of exposure will be categorized in months (<1, 1-<2, 2-<3, 3-<4, 4-<5, 5-<6, 6-<7, 7-<8, 8-<9, 9-<10, 10-<11, 11-<12, \geq 12 months) as well as in days (1-27, 28-55, 56-83, 84-111, 112-139, 140-167, 168-195, 196-223, 224-251, 252-279, 280-307, 308-335, \geq 336). Duration of exposure (months) will be calculated as ((Date of Last Dose – Date of First Dose) +1)/30.25. If date of last dose is unknown, then the date of last clinical visit will be used.

A listing including study drug administration information from the eCRF will be presented.

9.2. Treatment Compliance

Subjects are expected to take study medication once per day.

Treatment compliance, as a percentage, will be calculated as compliance (%) = (Sum of Study drug taken= Yes) / (number of days in study) x 100. The number of actual doses taken will be recorded on the eCRF.

Subjects will be considered compliant overall for study medication if the compliance is \geq 80%. Descriptive statistics (number of subjects, mean, SD, median, minimum, and maximum) for number of actual tablets taken, number of expected tablets taken, and treatment compliance will be summarized.

9.3. Adverse Events (AEs)

An AE is any untoward medical condition that occurs in a subject while participating in this clinical study. The AEs will be coded to system organ class (SOC) and preferred term (PT) using the MedDRA dictionary, version 25.0. The National Cancer Institute Common Terminology Criteria for Adverse Events (NCI-CTCAE), version 4.03 will be used to assess the severity of AEs.

All AEs that occur after the first study drug administration and up to 30 days after the subject's last study drug administration will be considered treatment-emergent adverse events (TEAEs).

This document is confidential.

Summaries will focus on the TEAEs (simply referred to as adverse events in summary tables). A subject with 2 or more TEAEs within the same level of summarization (i.e., SOC or PT) will be counted only once in that level using the most severe event or most related event.

Summaries presenting the frequency of AEs by SOC and PT will be sorted by descending frequency of SOC and then, within a SOC, by descending frequency of PT.

The following summary tables will be provided:

- 1) An overall summary with the number and percentage of patients reporting AEs, serious AEs, grade 3 or higher AEs, treatment-related AEs, AEs leading to study treatment discontinuation and AEs with outcome of deaths.
- 2) AEs and Treatment-Related Adverse Events (TRAEs) by maximum severity
- 3) AEs and Serious Adverse Events (SAEs) by maximum relatedness
- 4) AEs overall and by SOC and PT
- 5) AEs overall and by SOC, PT and highest CTCAE grade
- 6) TRAEs overall and by SOC and PT
- 7) TRAEs overall and by SOC, PT and highest CTCAE grade
- 8) AEs leading to study treatment termination overall and by SOC and PT
- 9) AEs leading to study treatment termination overall and by SOC and highest CTCAE grade
- 10) CTCAE Grade 3 or higher AEs, overall and by SOC and PT
- 11) SAEs overall and by SOC and PT

A SAE is an AE which falls into one or more of the following categories:

- a. Results in death
- b. Is life-threatening
- c. Requires inpatient hospitalization or prolongation of existing hospitalization
- d. Results in persistent or significant disability or incapacity
- e. Is a congenital anomaly/birth defect
- f. Is any other important medical event

- 12) SAEs overall and by SOC and PT and by age group (children 6-12 and adolescents 13-18)
- 13) Adverse Event of Special Interests (AESIs) overall and by SOC and PT

This document is confidential.

Adverse Events of Special Interest (AESI) for ecopipam include Convulsions, Depression and Suicide/Self Injury, Drug Abuse, Dependence and Withdrawal, Dyslipedaemia, Hepatic Disorders, Hyperglycaemia/New Onset Diabetes Mellitus, NMS, and Psychosis and Psychotic Disorders.

AESI for Parkinsonism include Ataxia, Confusional state, Coordination abnormal, Somnolence, Disturbance in attention, Dyskinesia, Hyperkinesia, Gait disturbance, Memory impairment, Tremor, Vertigo, Agitation, Anxiety, Disturbance in attention, Dystonia, Bradykinesia, Musculoskeletal stiffness, Dysstasia, Gait disturbance, Posture abnormal, Balance disorder, Movement disorder, Movement disorder, Dyskinesia, Muscle rigidity, Coordination abnormal, Muscle contracture, Bradykinesia, Gait disturbance, Terminal insomnia, Nightmare, Poor quality sleep, Sleep disorder, Fatigue, Dizziness, Balance disorder, Restlessness, Amnesia, Confusional state, Dementia, Mental impairment, Speech disorder, Dysphonia, Vocal cord dysfunction, Parosmia, Anosmia, Urinary incontinence, Anxiety, Apathy, Joint stiffness, Reduced facial expression, Confusional state, Flat affect, Constipation, Depression, Dysphagia, Drooling, Fall, Fear of falling, Loss of visual contrast sensitivity, Muscle tightness, Dysgraphia, Dyskinesia, and Weight decreased.

AESI summary tables are listed below:

- AESI for ecopipam overall and by system organ class and preferred term
- AESI for Parkinsonism overall and by system organ class and preferred term.

In this summary, a patient is counted once at the system organ class and once at each preferred term within the system organ class.

- 14) Most common AEs ($\geq 5\%$) first onset experienced during treatment period will be summarized by month and preferred term.
- 15) Most common AEs ($\geq 5\%$) new incidence or ongoing, experienced during treatment period will be summarized by month and preferred term.

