In the ITT population, after 30 days of treatment, Clinician Global Impression (CGI) Severity Scores decreased by $0.8~(\pm0.7)$ points on ecopipam and $0.2~(\pm0.9)$ points on placebo. Also, after ecopipam treatment, the percentages of subjects with much improved, minimally improved, no change, minimally worse CGI Improvement ratings were 40.00%, 15.00%, 20.00%, and 12.5%, respectively; while the percentages on placebo were 20.00%, 27.50%, 32.50%, and 12.50%, respectively. Similar results were observed in the Evaluable population. These data suggest that the subjects' disease severity decreased and that they had greater improvement while on ecopipam.

In the ITT population, the mean (\pm SD) DuPaul ADHD rating scale at baseline was 20.2 (\pm 11.6) points prior to ecopipam and 22.1 (\pm 11.3) points prior to placebo. On Day 30, ADHD Scores decreased by 1.9 (\pm 5.2) points on ecopipam and 2.7 (\pm 6.6) points on placebo. ADHD scales were almost unchanged after ecopipam treatment. Similar results were observed in the Evaluable population.

In the ITT population, the mean (\pm SD) YBOCS total scores at baseline were 5.7 (\pm 6.3) prior to ecopipam and 6.6 (\pm 6.9) prior to placebo. On Day 30 of the treatment period, YBOCS total scores decreased by 0.8 (\pm 3.3) points on ecopipam and 0.9 (\pm 4.1) points on placebo. The results of the obsession and compulsion subscales were similar to the total scores.

The results from the Safety population were the same as the ITT population.

A total of 149 treatment-emergent adverse events (TEAEs) were reported in 35 of the 40 treated subjects (87.50%). There was 1 serious TEAE during placebo treatment and 1 TEAE resulting in dose withdrawn permanently during ecopipam treatment. More patients on placebo had severe adverse events (7.5%) compared to ecopipam (5%). No TEAE resulted in death. There were 20 subjects (50.00%) reporting TEAEs related to study drug during ecopipam treatment and 10 subjects (25.00%) during placebo treatment. Forty percent (40.00%) of TEAEs were mild and 37.50% were moderate. One subject decreased the dosage due to fatigue one day after starting ecopipam. Another subject in the ecopipam group was discontinued from the study due to rash starting at Day 0 of the second treatment phase.

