7.4. Dose Adjustment Criteria

Doses will be adjusted based on the following weight bands to better achieve the 2 mg/kg/day target dose: ≥ 18 to ≤ 23 kg, > 23 to ≤ 34 kg, > 34 to ≤ 44 kg, > 44 to ≤ 68 kg, > 68 to ≤ 83 kg, > 83 kg. Dosing adjustments would be allowed down one dose level based on titration for safety reasons at the discretion of the Principal Investigator. See Section 10.5 for direction on administration of study drug.

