8.3. Subject Withdrawal Criteria

The Investigator or subject themselves may stop study treatment at any time for safety or personal reasons.

Any subject with a CDRS-R assessment indicative of the onset of a new depressive episode at any visit can be discontinued from study participation at the discretion of the Investigator. Any subject with a new positive response on questions 4 and/or 5 of the C-SSRS will be immediately discontinued and evaluated for risk. Dosing may be restarted at the discretion of the Investigator following consultation with the Sponsor or its designee.

Where possible, a subject who discontinues treatment will undergo the protocol-specified end-of study procedures at the time of discontinuation. Date and reason(s) of premature discontinuation will be described on the CRF. In addition, the date of last dose of study treatment will be recorded on the Study Treatment Dosing CRF.

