13.2. Planned Analyses

13.2.1. Safety Analysis

Adverse Events:

AEs, which include clinical laboratory test variables, will be documented from the time of the first study medication administration from the open label study until the subject's study participation is complete (study discontinuation and up to 30-days follow-up). All AEs that occur after the first study medication application and up to 30 days after the subject's last study medication application will be considered TEAEs.

Each AE will be reported with severity (mild, moderate, severe), seriousness, duration, resolution, action taken, and its relationship with the study medication (related or not related).

Adverse events will be summarized using system organ classification (SOC) defined by Medical Dictionary for Regulatory Activities (MedDRA); the following AEs will be categorized as AESIs in this study (AEs fitting under these categories to be fully described in the SAP):

- Extrapyramidal reactions (i.e. tardive dyskinesia, akathisia)
- Metabolic changes (hyperglycemia/diabetes mellitus, dyslipidemia, weight gain)
- Orthostatic hypotension
- Suicidality
- Leukopenia, neutropenia, agranulocytosis

TEAEs and AESIs will be summarized by severity and by relationship to study medication. Serious TEAEs and TEAEs leading to study termination will be summarized separately.

Other Safety Assessments:

Laboratory values, vital signs, ECG, and physical examination will be summarized descriptively by visit.

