3.1. Primary Objective

The primary objective of this study is to evaluate the long-term safety and tolerability of ecopipam tablets in pediatric subjects (aged ≥ 6 to ≤ 18 years at Baseline of the EBS-101-CL-001 study) with Tourette's Syndrome (TS) that were previously enrolled in the EBS-101-CL-001 study (Phase 2b) and completed the Phase 2b study.

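### AEs that lead to dose reduction or interruption are collected but not counted in any planned table, so the discontinuation rate alone cannot describe tolerability of the target dose

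*SAP*

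**What the plan says.** SAP 3.1 sets out to "evaluate the long-term safety and tolerability of ecopipam tablets in pediatric subjects"; Protocol 6.1 also names tolerability.

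The protocol foresees both reduced and interrupted dosing:
- Section 7.4: "Dosing adjustments would be allowed down one dose level based on titration for safety reasons at the discretion of the Principal Investigator".
- Sections 7.5 and 8.3 stop dosing after a new positive answer to C-SSRS question 4 or 5, and then add: "Dosing may be restarted at the discretion of the Investigator following consultation with the Sponsor or its designee".
- Section 12.2.1 makes the need to interrupt study drug one of the criteria for calling an abnormal test result an AE.
- Section 12.4 has the investigator record action taken, and Section 13.2.1 repeats it: "Each AE will be reported with severity (mild, moderate, severe), seriousness, duration, resolution, action taken".

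SAP 9.3 lists 15 summaries. Three are defined by action taken, and all three concern the end of treatment. Item 1, the overall table, includes "AEs leading to study treatment discontinuation and AEs with outcome of deaths". Item 8 is "AEs leading to study treatment termination overall and by SOC and PT". Item 9 is the same selection with CTCAE grade. Item 4, "AEs overall and by SOC and PT", takes in every treatment-emergent AE (TEAE). The SAP's index of tables matches this list (14.3.1.1, 14.3.1.5.1 and 14.3.1.5.2). It has no entry for AEs leading to reduction or interruption, or for subjects on a modified dose.

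**The concern.** A child who cannot tolerate the weight-band dose has two routes under this protocol: leave treatment, or stay on it at a lower dose or after a pause. The planned summaries by action taken count only the first. If the second is used often, the discontinuation rate can be low because doses were cut rather than because the 2 mg/kg/day target was tolerated, and the tables would not let a reader tell these apart. At stake is how well the report can support a tolerability statement about the target dose, which belongs to the primary objective.

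**Working it through.** Neither document states a sample size, target rate or power for tolerability, so there is no planned figure to reproduce. The check is whether any planned output would show a reduction or an interruption.

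**1. AE tables.** SAP 9.3 items 2-7 and 10-15 select by severity, relatedness, seriousness, special interest, or month of onset or presence. None selects by action taken. An AE that led to a reduction is included but cannot be picked out.

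**2. Exposure (SAP 6.2 and 9.1).** Duration = last dose date − first dose date + 1. A gap between those dates does not shorten it, and dose level does not enter.

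**3. Compliance (SAP 9.2).** Compliance = days with drug taken ÷ days in study × 100, and compliant means at least 80%. I take days in study as 336 (12 × 28, the start of the SAP's last exposure category) or 364 (52 × 7).
- Reduced dose taken every day: 336/336 = 100%.
- Assumed 28-day interruption: (336 − 28)/336 = 91.7%, or (364 − 28)/364 = 92.3%.
- Most missed days that still count as compliant: 67 of 336 (269/336 = 80.1%; 68 missed gives 79.8%), or 72 of 364 (292/364 = 80.2%; 73 missed gives 79.9%).

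**4. Tablet counts (SAP 9.2).** With the supplied strengths, 50 to 37.5, 75 to 50 and 100 to 75 mg can each remain one tablet. A step from 37.5 to 25 mg goes from one tablet to two (2 × 12.5). In the two heaviest bands the count can fall from two to one. Tablet number is therefore not a consistent marker of dose.

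**5. Size of one step.** I read one level down as the next lower step in Protocol Table 4. Reduction = 1 − lower/full.

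| Weight band (kg) | Full dose (mg) | One level down (mg) | Reduction |
|---|---|---|---|
| 18-23 | 37.5 | 25 | 33% |
| >23-34 | 50 | 37.5 | 25% |
| >34-44 | 75 | 50 | 33% |
| >44-68 | 100 | 75 | 25% |
| >68-83 | 150 | 100 | 33% |
| >83 | 200 | 100 | 50% |

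**6. Illustration from PSY302 (Protocol 5.2.2.1).** The protocol reports one permanent withdrawal for a TEAE on ecopipam among 40 subjects, and also: "One subject decreased the dosage due to fatigue one day after starting ecopipam". Withdrawal alone is 1/40 = 2.5% (exact 95% CI 0.1% to 13.2%). Withdrawal or reduction is 2/40 = 5.0% (0.6% to 16.9%), taking these as two different subjects, as the text implies.

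**7. Range under assumed rates.** If a proportion d stop for an AE and a separate proportion r are only reduced or interrupted, the share of dose-modifying cases absent from items 1, 8 and 9 is r/(d + r). With d of 5% to 10% and r of 2.5% to 20%, it runs from 0.025/0.125 = 20% to 0.20/0.25 = 80%. These rates are assumptions; no document gives them.

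**The case against.** A reader might infer that the AE tables count only events that end treatment, and that a child whose dose was cut is reported as having tolerated ecopipam. The documents do not support either reading. Most of the 15 summaries include TEAEs whatever action was taken. A dose cut for fatigue or somnolence would appear in the all-AE and severity tables and in the Parkinsonism special-interest table, which lists both terms. No endpoint or table classes a subject as tolerant or intolerant.

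Other points on that side also have weight:
- Protocol 13.2.1 promises separate summaries only for serious TEAEs and those leading to study termination. SAP 9.3 covers serious TEAEs and treatment termination and adds more, and Listings 16.2.7.1 (AEs) and 16.2.5.1 (study drug administration) are planned.
- Dosing is fixed by weight band with a permitted step down, so this is not a flexible-dose design in the usual sense.
- Restart is described only after the C-SSRS rule. Such events, if reported as AEs, fall under the depression and suicide/self-injury special-interest category, and C-SSRS is summarised by visit. SAP 9.3 does not say that termination means permanent, so whether a restarted subject is counted in items 8 and 9 is open rather than excluded.
- PSY302 was a 4-week crossover with a different dosing scheme, and one reduction there says little about a year of treatment.
- The documents do not show the action-taken categories on the CRF, or confirm that dose level is recorded.

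These points limit the claim but do not remove the gap. Listings give individual records without a count, and no planned summary turns a collected action-taken field into a number for reduction or interruption.

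**Conclusion.** This is a reporting gap that bears on the primary objective and is cheap to close. AEs leading to dose reduction or interruption are tabulated with all others but never identified as such, and exposure and compliance as defined do not reveal them. A permitted step is 25% to 50% less drug, and a four-week pause still scores about 92% compliance, so a low discontinuation rate alone would not establish that the target dose was tolerated.

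The conclusion rests on the SAP's listed outputs being complete and on reading one dose level as one step in Table 4. Its practical size is unknown: no rate of reduction or interruption can be derived for this study, and the PSY302 counts and the 20% to 80% range only illustrate. The material does not show that the planned tables misstate any AE rate, nor does it justify making a new composite the main basis for the tolerability conclusion.

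**What to change.** 1. In Table 14.3.1.1 and one table by system organ class and preferred term, add descriptive rows for TEAEs with action taken of dose reduced, of drug interrupted, and of any of reduced, interrupted or withdrawn.
2. State how a subject stopped and later restarted under the C-SSRS rule is counted in items 1, 8 and 9 and in the new rows. Align the wording at the same time: Protocol 13.2.1 and Listing 16.2.7.3 refer to study termination, while SAP 9.3 refers to treatment.
3. Where the dosing eCRF records dose level, add n (%) of subjects below their weight-band dose for safety, ever and at last dose.
4. Label these outputs post hoc. SAP Section 10 records additions made after database lock, and the table index already has a post-hoc block. Report them beside the discontinuation rate when describing tolerability, not as a replacement primary measure.

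The cost is a few rows and one or two tables. Items 1 and 3 depend on a check of the CRF: first the action-taken categories, then whether dose level was captured. The tolerability description may become somewhat less favourable.

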12.2.1.3. Other Adverse Event

Other AEs (OAEs) will be identified by the Drug Safety Physician and if applicable, also by the Clinical Study Team Physician, during the evaluation of safety data for the clinical study report. Significant AEs of particular clinical importance, other than SAEs and those AEs leading to discontinuation of the subject from the study, will be classified as OAEs. For each OAE, a

narrative may be written and included in the clinical study report. Adverse events of special interest (AESI) are listed in Section 13.2.1.

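### SAP 9.3 departs from the protocol's five AESI categories without declaring it: two are absent, two are only partly covered, and no AESI table is by severity or relationship

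*SAP*

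**What the plan says.** Protocol 13.2.1 introduces its list with "the following AEs will be categorized as AESIs in this study (AEs fitting under these categories to be fully described in the SAP". It then names five categories: "Extrapyramidal reactions (i.e. tardive dyskinesia, akathisia"), "Metabolic changes (hyperglycemia/diabetes mellitus, dyslipidemia, weight gain"), "Orthostatic hypotension", suicidality, and "Leukopenia, neutropenia, agranulocytosis". Protocol 12.2.1.3 points back to the same place: "Adverse events of special interest (AESI) are listed in Section 13.2.1". The display is also set: "TEAEs and AESIs will be summarized by severity and by relationship to study medication".

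SAP 9.3 uses two lists. The first reads "Adverse Events of Special Interest (AESI) for ecopipam include Convulsions, Depression and Suicide/Self Injury, Drug Abuse, Dependence and Withdrawal, Dyslipedaemia, Hepatic Disorders" and continues with hyperglycaemia/new-onset diabetes, NMS and psychosis, eight groups in all. No preferred terms are given under any of the eight. The second is a list of terms for Parkinsonism. There are two AESI tables, 14.3.1.8.1 (Parkinsonism) and 14.3.1.8.2 (ecopipam). Both in SAP 9.3 and in the table index they are by system organ class (SOC) and preferred term (PT) only.

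SAP Section 10 records the change to the mITT definition and then a series of items added after database lock. It does not mention AESIs.

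**The concern.** The protocol gave the SAP the task of saying which adverse events fall under each category. It did not give it the choice of categories. If the SAP is followed exactly, the AESI tables will not report two of the categories at all and will report two others without components that the protocol names.

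Long-term safety and tolerability is the primary objective, and the missing items are ones that the protocol itself raises. Section 5.3.2 says that extrapyramidal reactions appear much less frequent than with D2 antagonists, and it counts orthostatic hypotension among the possible advantages. Section 5.3.1 notes that orthostatic blood pressure changes were not documented in the older programme, and that almost all children in the earlier open-label extension gained weight. A reader of the study report would expect the AESI tables to address these topics and would have no notice that the list had changed.

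**Working it through.** No sample size or test statistic is involved, so the check sets the texts side by side.

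**Step 1: categories.** Each term in Protocol 13.2.1 was searched for in both SAP 9.3 lists (eight ecopipam groups; 64 Parkinsonism entries, of which 52 are distinct).

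| Protocol category | Found in the SAP lists | Not found | Status |
|---|---|---|---|
| Extrapyramidal reactions | Dyskinesia, tremor, dystonia, bradykinesia, muscle rigidity, movement disorder, restlessness | Akathisia, tardive dyskinesia | Partly covered |
| Metabolic changes | Hyperglycaemia/diabetes, dyslipidaemia | Weight gain (the only weight term is for a decrease) | Partly covered |
| Orthostatic hypotension | No hypotension term; only the non-specific dizziness | The category | Absent |
| Suicidality | Grouped with depression and self-injury | None | Kept |
| Leukopenia, neutropenia, agranulocytosis | No matching term | The category | Absent |

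Tally: 2 absent + 2 partly covered + 1 kept = 5.

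**Step 2: displays.** The protocol asks for AESIs by severity and by relationship. AESI tables by severity: 0 of 2. AESI tables by relationship: 0 of 2. SAP 9.3 does plan severity and relatedness displays, but for all adverse events, treatment-related events or serious events, not for AESIs.

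**Step 3: declaration.** Section 10 holds 1 entry on the mITT set and 17 post-lock items, so 1 + 17 = 18 entries. Entries on AESIs: 0 of 18. The section is otherwise detailed: it records an extra exposure table by days and two new adverse event tables by month.

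**Step 4: what remains visible elsewhere.**
- Tables 14.3.1.3.1 and 14.3.1.3.2 show every PT, overall and by highest CTCAE grade.
- Tables 14.3.1.4.1 and 14.3.1.4.2 do the same for treatment-related events.
- Listing 16.2.7.1 gives all adverse events, so distinct subjects in any protocol category can be counted from it.
- SAP 9.4 summarises haematology with shift tables. SAP 9.5 summarises supine and standing blood pressure, weight and BMI z-scores. SAP 9.8 summarises AIMS and BARS monthly.

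**The case against.** The best defence is that the protocol delegated the AESI detail to the SAP and that nothing is lost in substance. On delegation, the protocol's wording covers the events that fit under the stated categories. It does not extend to dropping a category or leaving out its named examples.

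On substance, much of the defence stands. Every event can be looked up by PT, grade and relatedness, direct measurements cover the omitted topics, and the Parkinsonism list holds many extrapyramidal terms, including tremor, which Protocol 5.3.1 itself calls an extrapyramidal reaction.

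It can also be said that an entry in Section 10 would be enough. That would restore traceability, but the AESI summaries by severity and relationship would still be missing.

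Some stronger readings are tempting, and the documents do not support them:
- *Safety signals would be missed.* Step 4 of the working shows otherwise.
- *A pre-specified subject count per category has been dropped.* The protocol never states such a count. It speaks of summarising adverse events by SOC, so the SOC and PT layout is not itself a departure. The missing severity and relationship displays are.
- *Most of the protocol's named components are gone.* Such a tally depends on how compound items are split. Keeping hyperglycaemia/diabetes and the three white-cell terms as one item each gives 5 of 8 not named; splitting both gives 7 of 11. Only the count by category is robust.
- *The AESI lists were altered after the data were seen.* Most of Section 10 concerns post-lock additions, but neither document says when the AESI lists were set.

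**Conclusion.** The point holds as a departure from the protocol that should be fixed. SAP 9.3 omits two of the five AESI categories, covers two in part and keeps one. Neither AESI table has the severity or relationship display that the protocol requires, and Section 10 is silent on all of this. The consequence is that protocol-specified AESI reporting, on the primary objective, is incomplete and the change cannot be traced. Detection of individual events is not impaired.

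This rests on reading the SAP lists as printed. Because the eight ecopipam groups have no preferred terms, one of them might in practice pick up a term such as weight gain. The SAP does not say so, which is a further reason to supply a term list.

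**What to change.** In SAP 9.3 and Tables 14.3.1.8.x:
- Restore the five protocol categories, each with defined preferred terms.
- Tabulate them by severity and by relationship. One distinct-subject count per category would be a sensible layout, since PT rows cannot be added when a subject appears in several, but the protocol does not state it.
- Keep the SAP's ecopipam groups and Parkinsonism list as additional summaries.

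In SAP Section 10, declare the change to the AESI lists and displays, its reason, and when it was made relative to database lock.

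The cost is SAP wording, a term list and a few more tables from data already collected. Output added after lock must be labelled as such, although the categories themselves were set in the protocol.

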The most common TEAEs during ecopipam treatment were headache (6 of 40), abdominal pain upper (4 of 40), nausea (4 of 40), vomiting (4 of 40), insomnia (4 of 40), and somnolence (4 of 40). The most common TEAEs during placebo treatment were nasopharyngitis (5 of 40), headache (5 of 40), abdominal pain upper (4 of 40), and diarrhea (4 of 40). The most common related TEAEs during ecopipam treatment were nausea (4 of 40) and somnolence (4 of 40). The most common related TEAEs during placebo treatment were headache (3 of 40), somnolence (2 of 40), and initial insomnia (2 of 40).

There was no evidence that administration of ecopipam affected weight, Children's Depression Inventory (CDI) scores or Columbia Suicide Severity Rating Scale (C-SSRS) in the subjects. There were no clinically significant laboratory abnormalities, changes in vital signs, ECG, or physical examination findings after ecopipam administration. There were no AEs related to extrapyramidal reactions.

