In subjects with TS, ecopipam has been evaluated in two studies, one study in adult subjects with TS and one study in children/adolescents with TS. In the pediatric TS study, overall, adverse events were more common in ecopipam compared to placebo. There were no serious adverse events (SAEs) and only one subject discontinued treatment due to an adverse event in the ecopipam group. Most adverse events were mild to moderate in severity. Adverse events in the Psychiatric Disorders, Central Nervous System Disorders and Gastrointestinal Disorders categories were more common with ecopipam than placebo. Notably, more subjects experienced adverse events of somnolence, insomnia, sedation, restlessness, irritability, nausea and vomiting with ecopipam than with placebo. There were no AEs of extrapyramidal symptoms in the pediatric study. A higher percentage of subjects on ecopipam gained 5 pounds or more during the study than with placebo (17.5% compared to 15%). Orthostatic blood pressure assessments were not done (or not reported). A table of weight changes was provided for the open-label extension study (PSY302A) and almost all of the children gained weight after 3, 6, 9 or 12 months of treatment. Suicidal ideation was seen both during the blinded study as well as the open-label extension study in pediatric subjects on ecopipam. There did not appear to be clinically significant ECG findings. However, open-label extension adverse event data have not yet been analyzed.

In the adult study in TS, the most commonly reported adverse events (incidence \geq 20%) were sedation (33%), insomnia (33%), fatigue (33%), somnolence (28%), headache (22%), muscle twitching (22%) and anxiety (22%). Two subjects developed adverse event of akathisia and one developed an adverse event of tremor, both of which are extrapyramidal reactions. Three of 18 subjects (16.7%) also discontinued study drug due to an adverse event.

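### The overall row of the Parkinsonism AESI table is non-specific, and no planned output counts subjects with any extrapyramidal adverse event

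*SAP*

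**What the plan says.** Protocol 13.2.1 names five categories of adverse events of special interest (AESI) and leaves the SAP to set out which events fall in each. The first is "Extrapyramidal reactions (i.e. tardive dyskinesia, akathisia").

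SAP 9.3 has two AESI groups, one for ecopipam and one for Parkinsonism. Neither is called extrapyramidal reactions. The ecopipam group covers convulsions, depression and self-injury, abuse and withdrawal, lipids, liver, glucose, neuroleptic malignant syndrome and psychosis, so the Parkinsonism group is the only one that could serve the protocol's extrapyramidal category.

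The Parkinsonism list opens "AESI for Parkinsonism include Ataxia, Confusional state, Coordination abnormal, Somnolence, Disturbance in attention, Dyskinesia, Hyperkinesia" and later includes "Fatigue, Dizziness, Balance disorder, Restlessness, Amnesia", "Parosmia, Anosmia, Urinary incontinence, Anxiety, Apathy" and "Constipation, Depression, Dysphagia, Drooling, Fall". Tremor, dystonia, bradykinesia and muscle rigidity are on the same list. The planned table (14.3.1.8.1) is "AESI for Parkinsonism overall and by system organ class and preferred term", with a patient counted once per system organ class and once per preferred term. No motor-only subset is defined.

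**The concern.** One event of any listed term puts a child in the overall row. Several listed terms are common events in the protocol's own summaries of earlier ecopipam studies, and Protocol 5.1 names anxiety and depression as common comorbid conditions in Tourette's syndrome. The trial is open-label with no control arm, so a background rate cannot be subtracted.

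Long-term safety is the primary objective, and Protocol 5.3.2 puts forward a lower rate of extrapyramidal reactions than with D2 antagonists as a safety advantage. Two things are at stake. A row headed Parkinsonism could show a sizeable percentage made up of non-motor events. And the figure that bears on the claimed advantage, subjects with at least one extrapyramidal event, is not produced anywhere.

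**Working it through.** The plan states no expected rate for this group, so there is no planned figure to reproduce. The checks below use the list itself and the rates quoted in the protocol.

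**1. Composition of the list (SAP 9.3).**
- There are 64 entries. Three terms appear three times and six appear twice, which gives 3 × 2 + 6 × 1 = 12 surplus entries and 64 − 12 = 52 distinct terms. The repeats do not affect counts.
- Narrow reading of movement, 9 terms: dyskinesia, hyperkinesia, tremor, dystonia, bradykinesia, movement disorder, muscle rigidity, reduced facial expression, drooling. That leaves 43/52 = 83% non-movement.
- Broad reading, 21 terms, adding gait, balance, coordination, stiffness, posture and restlessness terms and similar. That leaves 31/52 = 60% non-movement.
- Akathisia and tardive dyskinesia are absent from the list.

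**2. Floor for the overall row.** The share of subjects with any listed term is at least the rate of the most frequent single listed term.

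| Source in protocol | Listed non-movement terms | Floor | Sum if no subject had two |
|---|---|---|---|
| PSY302, pediatric Tourette's (5.2.2.1) | somnolence 4/40 | 10% | – |
| Phase 3 obesity, adults, 52 weeks (5.2.2.1) | depression 236, somnolence 216, fatigue 215, anxiety 211, of 1482 | 236/1482 = 16% | 878/1482 = 59% |
| Adult Tourette's, n = 18 (5.3.1) | fatigue 33%, somnolence 28%, anxiety 22% (6, 5 and 4 subjects) | 6/18 = 33% | 15/18 = 83% |

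For PSY302 the protocol reports "There were no AEs related to extrapyramidal reactions". That is 0/40, with exact two-sided 95% upper limit 1 − 0.025^(1/40) = 8.8%. The row would still read at least 10%.

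**3. How much of the row would be non-motor.** Let b be the share with a listed non-movement term and q the share with a movement term, assumed independent. The row is 1 − (1 − b)(1 − q), and the fraction of its subjects with no movement term is b(1 − q) divided by the row.
- b = 10% (pediatric floor), q = 2%: row 11.8%, fraction 0.098/0.118 = 83%.
- b = 10%, q = 5%: row 14.5%, fraction 66%.
- b = 10%, q = 8.8%: row 17.9%, fraction 51%.

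The adult values of b give larger fractions at each q. At b = 10%, doubling q from 2% to 4% moves the row from 11.8% to 13.6%.

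**4. Background.** In the cocaine-dependence study (Protocol 5.2.2.1), somnolence occurred in 19/93 = 20% on placebo. By this list, about one placebo subject in five would be a case.

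**5. The missing count.** Preferred-term rows cannot be added to give subjects with any extrapyramidal event, because one subject may appear in several. The list is also incomplete for the protocol's category. In the adult Tourette's study, two subjects had akathisia and one had tremor, and only tremor is listed. The list would capture 1/18 = 5.6% of subjects with an extrapyramidal event, against 3/18 = 16.7% if the three subjects are distinct.

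**The case against.** The strongest reply is that the plan does not rely on the overall row. Table 14.3.1.8.1 also has preferred-term rows, Listing 16.2.7.5 lists the individual events, all adverse events are tabulated by term and by grade, and AIMS and BARS are summarized at Baseline and monthly. The SAP attaches no hypothesis, threshold or comparison to the overall row and does not call it the extrapyramidal rate. A deliberately broad screen with term-level detail is a legitimate choice, and which non-motor features belong in it is a clinical question that the documents do not settle.

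Most of this stands. A reader might infer that a real motor signal would be lost among sedation events, or that the study cannot assess extrapyramidal risk. The documents do not support either reading, because the outputs above would show motor events. A reader might also take 59% or 83% as likely values. They are ceilings that assume no subject had two terms, and they come from adults. This study takes only completers of the parent trial and excludes a major depressive episode in the past two years. Depression, anxiety and fatigue are not among the most common ecopipam events reported for PSY302. That the row will consist mostly of sedation and mood events is a forecast, not a fact, and sedation itself is not on the list.

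The reply does not supply the missing number. Term rows cannot be summed, AIMS and BARS summarize scores rather than event incidence, and akathisia, if reported as an event, would fall outside the Parkinsonism table and its listing.

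**Conclusion.** The concern holds in a limited form. The overall row of Table 14.3.1.8.1 is non-specific: 60% to 83% of its terms are not movement terms, and on the protocol's pediatric data it would be at least 10% with no extrapyramidal events reported. Adult data suggest it could be higher, with floors of 16% and 33%, but those populations differ. No planned output gives the number of subjects with any extrapyramidal adverse event, although Protocol 13.2.1 makes that an AESI category, and the two conditions named there are not on the list.

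This rests on point rates from other studies, populations and doses, and on a reading of which terms are motor, for which both ends of the range are shown. The split in step 3 of the working also assumes independence and a motor rate between 2% and 8.8%. The term count and the missing subject-level figure need none of these rates. The consequence is a gap in reporting that existing data can close; it does not leave the study blind to motor effects.

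**What to change.** In SAP 9.3 and Table 14.3.1.8.1, add a listed extrapyramidal/motor subset made up of the motor terms already on the list plus akathisia and tardive dyskinesia. Consider restlessness for inclusion: it is already on the broad list, and Protocol 5.3.1 says it was more frequent on ecopipam than placebo in children. A medical reviewer should settle the borderline terms (gait, balance, coordination, stiffness).

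Give the subset its own row counting subjects with at least one such event, with an exact (Clopper-Pearson) 95% confidence interval. Report the extrapyramidal rate from that row, not from the broad one. Keep the broad list as a supplementary sensitive screen, so that non-motor features stay visible.

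The cost is SAP wording, one subtotal row and its interval, with no new data. SAP Section 10 records that updates were already made after database lock, so the subset must be labelled post hoc. The index of tables already has a post-hoc block.
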